6.6 Dose Modification

In case a dose reduction is necessary, the study treatment will be administered according to the following tables. [Table 6-1](#) shows the dose modification levels for regorafenib. [Table 6-2](#), [Table 6-3](#), [Table 6-4](#), and [Table 6-5](#) show the dose modification plans for specific known drug-related toxicities.

Table 6-1: Dose modification levels for regorafenib

Dose Level	Daily Dose	Number of tablets
Dose level 0 (standard dose)	160 mg	4 tablets of regorafenib, 40 mg-tablet
Dose level -1	120 mg	3 tablets of regorafenib, 40 mg-tablet
Dose level -2	80 mg	2 tablets of regorafenib, 40 mg-tablet

Table 6-2: Dose Modification/Delay for Toxicities Related to Study Drug (Except Hand Foot Skin Reaction, Hypertension, and ALT and/or AST increases)^{a,c}

Grade of Event	Dose Interruption	Dose modification	Dose for subsequent cycles
Grade 0-2	Treat on time	No change	No change
Grade 3	Delay until \leq Grade 2 ^b	Reduce 1 dose level	If toxicity remains \leq Grade 2, dose re-escalation can be considered at the discretion of the treating investigator. If dose is re-escalated and toxicity (\leq Grade 3) recurs, institute permanent dose reduction.
Grade 4	Delay until \leq Grade 2 ^b	Reduce by 1 dose level. Permanent discontinuation can be considered at treating investigator's discretion.	

Abbreviations: ALT – alanine transaminase; AST – aspartate transaminase

a Excludes alopecia, non-refractory nausea/vomiting, non-refractory hypersensitivity, non-clinically significant and asymptomatic laboratory abnormalities.

b If no recovery after a 4-week delay, treatment should be permanently discontinued. In the event of severe bleeding necessitating urgent medical intervention, permanent discontinuation of regorafenib should be considered.

c In subjects who develop cardiac ischemia and/or infarction, interruption of regorafenib is recommended until resolution. The decision to re-initiate regorafenib therapy should be based on careful consideration of the potential benefits and risks of the individual subject. Regorafenib should be permanently discontinued if there is no resolution.

Table 6-3: Dose modifications for HFSR related to regorafenib (dose expansion phase) ("Palmar-plantar erythrodysesthesia syndrome")

Skin toxicity grade	Occurrence	Recommended dose modification and measures

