Grade 1: Numbness, dysesthesia, paresthesia, tingling, painless swelling, erythema or discomfort of the hands or feet which does not disrupt the subject's normal activities	Any	Maintain dose level and immediately institute supportive measures for symptomatic relief.
Grade 2: Painful erythema and swelling of the hands or feet and/or discomfort which affects the subject's normal activities.	1 st occurrence	Decrease dose by 40 mg (one tablet) and immediately institute supportive measures. If no improvement occurs despite dose reduction, interrupt therapy for a minimum of 7 days, until toxicity resolves to Grade 0-1. A dose re-escalation is permitted at the discretion of the treating physician.
	No improvement within 7 days or 2 nd occurrence	Interrupt therapy until toxicity resolves to Grade 0-1. When resuming treatment, decrease dose by 40 mg (one tablet). A dose re-escalation is permitted at the discretion of the treating physician.
	3 rd occurrence	Interrupt therapy until toxicity resolves to Grade 0-1. When resuming treatment, decrease dose by 40 mg (one tablet). A dose re-escalation is permitted at the discretion of the treating physician.
	4 th occurrence	Discontinue treatment.
Grade 3: Moist desquamation, ulceration, blistering or severe pain of the hands or feet, or severe discomfort that causes the subject to be unable to work or perform activities of daily living.	1 st occurrence	Institute supportive measures immediately. Interrupt therapy for a minimum of 7 days until toxicity resolves to Grade 0-1. When resuming treatment, decrease dose by 40 mg (one tablet). A dose re-escalation is permitted at the discretion of the treating physician.
	2 nd occurrence	Institute supportive measures immediately. Interrupt therapy for a minimum of 7 days until toxicity resolves to Grade 0-1. When resuming treatment, decrease dose by 40 mg (one tablet).
	3 rd occurrence	Discontinue treatment.

Abbreviations: HFSR – hand-foot-skin reaction

Table 6-4: Recommended dose modification and measures for hypertension

Hypertension grade	Occurrence	Recommended dose modification and measures ^a
Grade 1	Any	Maintain dose level. Consider increased BP monitoring.

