Grade 2	Any	Institute antihypertensive treatment with the aim to achieve diastolic BP \leq 90 mmHg: 
 • If BP previously within normal limits, start antihypertensive monotherapy. • If subject already on antihypertensive medication, titrate up the dose. Continue regorafenib, or if symptomatic, hold regorafenib until symptoms resolve AND diastolic BP \leq 90 mmHg. ^b When regorafenib is restarted, continue at the same dose level.
Grade 3	First occurrence	Institute antihypertensive treatment with the aim to achieve diastolic BP \leq 90 mmHg: 
 • Start antihypertensive medication AND/OR 
 • Increase current antihypertensive medication AND/OR 
 • Add additional antihypertensive medications. Hold regorafenib until diastolic BP \leq 90 mm Hg, and if symptomatic, until symptoms resolve. ^b When regorafenib is restarted, continue at the same dose level. If BP is not controlled with the addition of new or more intensive therapy, reduce by 1 dose level. ^c
	Re-occurrence	If Grade 3 hypertension recurs despite dose reduction and antihypertensive therapy, reduce another dose level. ^d
Grade 4	Any	Discontinue therapy

Abbreviations: BP = blood pressure.

a A more conservative management of hypertension is allowed if judged medically appropriate by the investigator.

b Subjects requiring a delay of >4 weeks should go off regorafenib.

c If BP remains controlled for at least one full cycle, dose re-escalation is permitted at the investigator's discretion.

d Subjects requiring >2 dose level reductions (<80 mg reduction) should go off regorafenib.

Table 6-5: Dose modification/interruption for ALT/AST increases related to regorafenib

Observed elevations of ALT and / or AST	Occurrence	Recommended measures and dose modification
≤5 times ULN	Any occurrence	Continue regorafenib treatment. Monitor liver function weekly until transaminases return to <3 times ULN or baseline.
>5 times ULN to ≤20 times ULN	1 st occurrence	Interrupt regorafenib treatment. Monitor transaminases weekly until return to <3 times ULN or baseline. Restart: If the potential benefit outweighs the risk of hepatotoxicity, re-initiate regorafenib treatment, reduce dose by 40 mg (one tablet), and monitor liver function weekly for at least 4 weeks.
	Re-occurrence	Discontinue treatment with regorafenib permanently.

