>20 times ULN	Any occurrence	Discontinue treatment with regorafenib permanently.
>3 times ULN with concurrent bilirubin >2 times ULN	Any occurrence	Discontinue treatment with regorafenib permanently. Monitor liver function weekly until resolution or return to baseline. Exception: patients with Gilbert's syndrome who develop elevated transaminases should be managed as per the above outlined recommendations for the respective observed elevation of ALT and / or AST.

Abbreviations: ALT – alanine transaminase; AST – aspartate transaminase; ULN = upper limit of normal.

If a dose reduction has been performed within this study protocol intra subject dose reescalation can be considered up to the starting dose in this rollover study protocol at the discretion of the treating physician.

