7.1 Discontinuation of Study Intervention

In rare instances, it may be necessary for a patient to permanently discontinue study intervention. If study intervention is permanently discontinued, the participant will not remain in the study. See the SOA for data to be collected at the time of discontinuation of study intervention.

Patients *must* be withdrawn from the study intervention for the following reasons:

- At their own request or at the request of their legally acceptable representative. At any time during the study and without giving reasons, a subject may decline to participate further. The subject will not suffer any disadvantage as a result.

- If, in the investigator's opinion, continuation of the study would be harmful to the subject's well-being.
- At the specific request of the sponsor and in liaison with the investigator (e.g. obvious non-compliance, safety concerns).
- Severe allergic reactions, such as exfoliate erythroderma, anaphylaxis, or vascular collapse.
- Any other potential adverse reaction deemed sufficiently serious to warrant discontinuation of treatment by either the investigator or his designated associate(s).
- Substantial non-compliance with the requirements of the study.
- Use of illicit drugs or other substances that may, in the opinion of the investigator, have a reasonable chance of contributing to toxicity.
- Development of any intercurrent illness or situation which would, in the judgment of the investigator, may affect assessments of clinical status and study endpoints to a relevant degree.
- Clinical progression (e.g. defined as worsening of the ECOG PS ≥ 3 or symptomatic deterioration including increase in liver function tests).
- The development of a second malignancy.
- Subject lost to follow-up.
- Interruption in study drug administration for greater than 28 consecutive days (including the 1 week drug holiday in each cycle).
- More than 2 dose reductions of the study drug are necessary.

Patients with a beta-human chorionic gonadotropin (hCG) test consistent with pregnancy. Pregnancy will be reported as an SAE using the Pregnancy Monitoring Form.

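### The closing sentence of Protocol 6.6 allows re-escalation after any reduction; read literally, it contradicts the permanent reduction in Table 6-2 and omits a condition in Table 6-4

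*Protocol*

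**What the plan says.** Protocol Section 6.6 opens by sending sites to the tables: "In case a dose reduction is necessary, the study treatment will be administered according to the following tables". Each table then treats re-escalation in its own way.

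- **Table 6-2** (toxicities other than hand-foot skin reaction, hypertension and ALT/AST increases). After a Grade 3 event, re-escalation may be considered while toxicity stays at Grade 2 or below. If toxicity recurs after re-escalation, the instruction is to "institute permanent dose reduction".
- **Table 6-3** (hand-foot skin reaction). The rows for the first, second and third Grade 2 occurrence and for the first Grade 3 occurrence each say "A dose re-escalation is permitted at the discretion of the treating physician". The row for the second Grade 3 occurrence lacks that line.
- **Table 6-4, footnote c** (reduction for Grade 3 hypertension). "If BP remains controlled for at least one full cycle, dose re-escalation is permitted at the investigator's discretion".
- **Table 6-5** (ALT/AST). Restart is 40 mg lower. Re-escalation is not mentioned.

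Directly below Table 6-5 stands a general sentence. For any participant whose dose was lowered during the rollover study, it says that "intra subject dose reescalation can be considered up to the starting dose in this rollover study protocol at the discretion of the treating physician".

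Section 7.1 requires withdrawal from study intervention if "More than 2 dose reductions of the study drug are necessary". Section 7.1.2 refers rechallenge back to Section 6.6.

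**The concern.** The general sentence has one trigger, that a reduction was made in this study, and one ceiling, the dose at which the participant entered the rollover study. It does not confine itself to cases where a table permits re-escalation. A reduction cannot be permanent and also reversible at the physician's discretion, so on its plain wording the sentence undoes the Table 6-2 instruction. It also offers re-escalation without the waiting condition that Table 6-4 footnote c attaches.

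This concerns individual dosing after Grade 3 toxicity. Section 8 allows no waivers and treats adherence as essential, yet a site cannot tell from Section 6.6 which rule it must follow.

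There is a smaller consequence for the data. Frequency of dose modifications is the endpoint for the secondary objective (Protocol Section 3), and SAP 6.3 summarises the number of modifications. AEs that lead to dose reduction are among the events collected for the safety endpoint (Schedule of Activities). Two sites reading Section 6.6 differently could record different counts from the same clinical course.

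**Working it through.** The plan gives no figure to reproduce, and the study is descriptive (Protocol 9.1, 9.2). The check sets the texts side by side and follows one dose path.

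**Step 1. Closing sentence against each table**

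| Place | What the table says on re-escalation | Relation to the closing sentence |
|---|---|---|
| Table 6-2, recurrence after re-escalation | Reduction becomes permanent | Direct conflict if the sentence is read literally |
| Table 6-3, Grade 2 first to third occurrence; Grade 3 first occurrence | Expressly permitted | No conflict |
| Table 6-3, Grade 3 second occurrence | Silent | Ambiguous |
| Table 6-4, footnote c | Permitted after at least one full cycle of controlled blood pressure | Condition missing from the sentence |
| Table 6-5, restart after the 40 mg reduction | Silent | Ambiguous; the sentence is the only text |

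**Step 2. Dose path**

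Inputs: Table 6-1 levels of 160, 120 and 80 mg; an entrant at 160 mg; a Grade 3 toxicity covered by Table 6-2.

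1. Grade 3 toxicity at 160 mg: reduce to 120 mg (reduction 1).
2. Toxicity stays at Grade 2 or below: re-escalate to 160 mg (re-escalation 1).
3. Grade 3 toxicity recurs at 160 mg: reduce to 120 mg (reduction 2).

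Under Table 6-2 the path ends here: 160→120→160→120, with 2 reductions + 1 re-escalation = 3 dose changes. Under the literal closing sentence, 160 mg may be considered again: 160→120→160→120→160, with 2 reductions + 2 re-escalations = 4 dose changes. The difference is 4 − 3 = 1 dose change, to a level where the toxicity has occurred twice.

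A 120 mg entrant can follow the same pattern (120→80→120→80). Table 6-1 lists no level below 80 mg, so the example is not carried further down.

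**Step 3. Does Section 7.1 block the return?**

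Its trigger is more than 2 reductions. After step 3 the count is 2 if reduction events are counted. It is 1 if levels below the starting dose are counted, since 120 mg is one level below 160 mg. Neither exceeds 2, so the return is not blocked on either count.

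**Step 4. If toxicity then occurs a third time at 160 mg**

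Counting events, a third reduction becomes necessary and Section 7.1 requires withdrawal. Counting levels, the participant would again be one level down and withdrawal would not follow. Section 7.1 does not say which count it means. Table 6-4 footnote d speaks of dose-level reductions.

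**Step 5. Is there a rule of precedence?**

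The opening of Section 6.6 points to the tables but does not rank them against the later sentence. Section 7.1.2 points to Section 6.6 as a whole, which contains both. No other passage settles it.

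**The case against.** The strongest reply is that the sentence is only a ceiling. Section 6.6 opens by making the tables govern. The closing sentence is permissive and adds something the tables lack: how far a dose may be raised again. Participants enter at the dose of their last feeder-study cycle, so a cap at that entry dose has a natural purpose. On this reading the tables decide whether to re-escalate, the sentence decides how far, and nothing conflicts. The reading is plausible, but the text does not state it. It also gives a different answer from the literal reading in the Table 6-2 case, and in Table 6-5, where a ceiling alone would grant no permission.

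On Table 6-4 the reply is stronger. The sentence is silent on timing, so a site can satisfy both texts by waiting the full cycle. What remains is an omitted condition, not an overridden prohibition.

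It is also fair to say that discretion already produces variation. Tables 6-2, 6-3 and 6-4 leave re-escalation to the physician, so modification counts will differ between sites anyway. The SAP expects few patients and summarises only. The endpoint effect is therefore secondary to the dosing question.

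A reader might go on to infer four stronger things, none of which the documents support:

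- **That Table 6-3 is contradicted.** Four of its rows expressly permit re-escalation, and the second Grade 3 row only omits the permission.
- **That only the closing sentence allows return to a dose that has failed.** The Grade 2 rows of Table 6-3 already allow it.
- **That the literal reading forces withdrawal.** This needs a third occurrence, and it needs Section 7.1 to count events and not levels.
- **That it adds two or more dose changes.** The path shows one. On the event count, a further recurrence adds a discontinuation, not a further reduction.

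**Conclusion.** The point stands in a narrow form. Read literally, the closing sentence of Section 6.6 contradicts the permanent reduction in Table 6-2, and it leaves out the condition in Table 6-4 footnote c. In Table 6-5 and in the second Grade 3 row of Table 6-3 there is no contradiction, only doubt about whether the sentence applies.

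For a participant on the traced path the size is one further dose change, back to a level at which Grade 3 toxicity has already occurred twice. This rests on the sentence being read without an implied limit to what the tables allow. It does not depend on how Section 7.1 counts reductions. How often it would arise cannot be estimated from the documents. No hypothesis test, sample size or stated figure changes. The possible effect on the secondary endpoint is inconsistent counting between sites.

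It should be corrected because it concerns dosing after severe toxicity and the remedy is small.

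**What to change.** The sponsor should reconcile the paragraph after Table 6-5 with Table 6-2 and with Table 6-4 footnote c, and state in Section 6.6 which text governs where they differ. The same wording should say whether the sentence applies where a table is silent, namely in Table 6-5 and in the second Grade 3 row of Table 6-3. If the sentence was meant only as a ceiling, saying so would remove the conflict. If it was meant as a general permission, the table entries need to be changed to match. Which rule is clinically right is for the sponsor to decide.

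The cost is about one sentence, with table wording if needed, in a protocol amendment. It needs no new procedure, visit or data item. If the tables are chosen to govern, investigators lose some discretion in the affected rows.

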6.7 Intervention after the End of the Study

There is no planned intervention following the end of the study.

7. Discontinuation of Study Intervention and Participant Discontinuation/Withdrawal

7.1 Discontinuation of Study Intervention

In rare instances, it may be necessary for a patient to permanently discontinue study intervention. If study intervention is permanently discontinued, the participant will not remain in the study. See the SOA for data to be collected at the time of discontinuation of study intervention.

Patients *must* be withdrawn from the study intervention for the following reasons:

- At their own request or at the request of their legally acceptable representative. At any time during the study and without giving reasons, a subject may decline to participate further. The subject will not suffer any disadvantage as a result.

- If, in the investigator's opinion, continuation of the study would be harmful to the subject's well-being.
- At the specific request of the sponsor and in liaison with the investigator (e.g. obvious non-compliance, safety concerns).
- Severe allergic reactions, such as exfoliate erythroderma, anaphylaxis, or vascular collapse.
- Any other potential adverse reaction deemed sufficiently serious to warrant discontinuation of treatment by either the investigator or his designated associate(s).
- Substantial non-compliance with the requirements of the study.
- Use of illicit drugs or other substances that may, in the opinion of the investigator, have a reasonable chance of contributing to toxicity.
- Development of any intercurrent illness or situation which would, in the judgment of the investigator, may affect assessments of clinical status and study endpoints to a relevant degree.
- Clinical progression (e.g. defined as worsening of the ECOG PS ≥ 3 or symptomatic deterioration including increase in liver function tests).
- The development of a second malignancy.
- Subject lost to follow-up.
- Interruption in study drug administration for greater than 28 consecutive days (including the 1 week drug holiday in each cycle).
- More than 2 dose reductions of the study drug are necessary.

Patients with a beta-human chorionic gonadotropin (hCG) test consistent with pregnancy. Pregnancy will be reported as an SAE using the Pregnancy Monitoring Form.

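### Table 6-3 prescribes a third 40 mg decrease for Grade 2 hand-foot skin reaction where section 7.1 requires withdrawal, and Table 6-1 has no lower step for participants entering at 80 or 60 mg

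*Protocol*

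**What the plan says.** **The limit.** Protocol section 7.1 lists reasons for which patients must be withdrawn from study treatment. One is "More than 2 dose reductions of the study drug are necessary". It does not say whether this counts reduction events or net levels below the starting dose.

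**The HFSR schedule.** Section 6.6 introduces its tables with "In case a dose reduction is necessary, the study treatment will be administered according to the following tables". In Table 6-3, the Grade 2 row for the first occurrence says "Decrease dose by 40 mg (one tablet) and immediately institute supportive measures". The next row covers either "No improvement within 7 days" or a second occurrence, and the one after it covers the third occurrence. Both say "Interrupt therapy until toxicity resolves to Grade 0-1. When resuming treatment, decrease dose by 40 mg (one tablet". Treatment stops at the fourth occurrence. Each of the three decrease rows permits re-escalation at the physician's discretion, and 6.6 caps re-escalation at the rollover starting dose. The action column is headed "Recommended dose modification and measures".

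**The dose levels.** Section 6 admits participants at 60, 80, 120 or 160 mg. Table 6-1 lists 160, 120 and 80 mg and states no minimum. Table 6-2 says "Reduce 1 dose level" for a Grade 3 toxicity. Table 6-4 says "If BP is not controlled with the addition of new or more intensive therapy, reduce by 1 dose level". Tables 6-3 and 6-5 work in 40 mg steps instead. Footnote d of Table 6-4 takes a patient off drug after more than two level reductions, but it applies only to hypertension.

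**The concern.** The Grade 2 rows prescribe one more decrease than 7.1 allows. The Grade 3 HFSR rows prescribe two decreases and then stop, which fits 7.1, as does a Table 6-1 with exactly two levels below 160 mg. The title of Table 6-3 refers to a dose expansion phase, which this study does not have, so the table may have been carried over without being reconciled.

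At the third decrease, one instruction ends treatment and the other continues it at a dose Table 6-1 does not list. The first cannot readily be undone: under 7.1 a participant who permanently stops leaves the study, and exclusion criterion 4 bars anyone previously discontinued for good. The second continues regorafenib after repeated skin toxicity. Section 8 allows no protocol waivers.

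For entrants at 80 or 60 mg the difficulty comes earlier, at the first reduction.

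Reporting is a lesser matter. The same clinical event could appear as a dose modification (the secondary endpoint; SAP 6.3) at one site and as an event leading to discontinuation (SAP 6.6) at another.

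**Working it through.** The plan gives no figure to reproduce. The check counts the prescribed decreases and follows the dose.

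**Inputs.** Limit of 2 reductions (7.1). One 40 mg decrease in each of three Grade 2 rows (Table 6-3). Listed levels 160, 120 and 80 mg (Table 6-1). Entry doses 160, 120, 80 and 60 mg (section 6).

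**Step 1: count.** Decreases at occurrences 1, 2 and 3 make 3 events before the stop at occurrence 4. Since 3 > 2, the third decrease falls where 7.1 requires withdrawal.

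**Step 2: re-escalation.** Suppose r re-escalations of one level each occur before the third decrease. The net number of levels down afterwards is 3 − r:

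- r = 0: 3, over the limit
- r = 1: 2, at the limit
- r = 2: 1, within it

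On an event count the total is 3 whatever r is. So without re-escalation the conflict arises on either count; with it, the answer depends on a definition that 7.1 does not give.

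**Step 3: dose.** Dose after k steps without re-escalation = entry dose − 40k.

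| Entry (mg) | k = 1 | k = 2 | k = 3 |
|---|---|---|---|
| 160 | 120, listed | 80, listed | 40, unlisted |
| 120 | 80, listed | 40, unlisted | 0 |
| 80 | 40, unlisted | 0 | none |
| 60 (itself unlisted) | 20, unlisted | none (60 − 80 = −20) | none |

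The first step lands on a listed level for 2 of 4 entry doses (160 and 120). The two steps that 7.1 allows end on a listed level for 1 of 4 (160 → 80). The number of steps that stay at or above 80 mg is 2, 1, 0 and 0 for entry at 160, 120, 80 and 60 mg.

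**Step 4: level-based instructions.** Tables 6-2 and 6-4 reduce by level, not by milligrams. From 80 mg, the lowest level, and from 60 mg, not a level at all, Table 6-1 gives no next dose.

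**The case against.** **The texts can be read together.** Section 7.1 is mandatory, while the Table 6-3 column is headed as a recommendation. On this reading 7.1 is a general cap, and the third-occurrence row serves participants who have been re-escalated. This has force: it is probably the intended reading, and it means a careful site is not without guidance. But 6.6 says that treatment follows the tables, no text says which section prevails, and the row is not conditional on earlier re-escalation.

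**Table 6-1 may simply end at 80 mg.** A patient needing less would then stop. Footnote d of Table 6-4 probably intends this, although its bracketed wording is unclear. The reading is natural, but it is not stated for the other toxicities, and it does not fit a study that admits participants at 60 mg. The Schedule of Activities says dosing follows the feeder protocol, which may supply lower levels. Section 6.6 does not refer to that note, and the feeder protocols are not available here, so this cannot be settled.

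**Inferences to avoid.**

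- A reader might count four decreases by treating non-improvement and the second occurrence separately. The documents do not support this: they are alternative triggers in one row with one decrease, and the first-occurrence row already handles non-improvement by interruption. Four steps from 160 mg would also leave 160 − 160 = 0 mg.
- A reader might infer that only Table 6-3 can exceed the limit. Table 6-2 sets no maximum number of events, so separate toxicities could also call for a third reduction. What is particular to the Grade 2 HFSR rows is that they write the third decrease out and place the stop after it.

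**The effect is small.** Participants enter on a dose they have tolerated, the SAP expects few patients, and the tables will describe correctly whatever each site did. All of this stands and limits the weight of the point.

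**Conclusion.** The point holds as an inconsistency in the protocol text. Without re-escalation, the Grade 2 HFSR rows prescribe 3 decreases against a limit of 2, and from 160 mg the third gives 40 mg, half the lowest listed level. Separately, reducing by one dose level has no listed result for 2 of the 4 permitted entry doses.

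This rests on three assumptions: each Table 6-3 row is applied once; re-escalation is optional, as written; and no feeder protocol rule overrides 6.6. If feeder protocols do define lower levels, the dose-floor part shrinks to a missing cross-reference. The conflict over the third decrease remains unless they also replace Table 6-3.

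How often this will occur is unknown, and probably seldom. A reader might infer that the safety results are compromised. The documents do not support that: the analysis is descriptive, no hypothesis is tested, and any effect on reporting is limited to how a few events are classified. It is worth correcting for patient management, and because future feeder studies may bring in more participants under the same rules.

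**What to change.** 1. **Section 7.1.** Define the limit once: withdraw when the dose would fall more than two net levels below the rollover starting dose. Use the same wording in footnote d of Table 6-4.
2. **Table 6-3, Grade 2, second- and third-occurrence rows.** Add: *Discontinue if the decrease would exceed the section 7.1 limit or take the dose below the Table 6-1 minimum.* Because the rows refer to 7.1 and do not restate a count, the rule is kept in one place.
3. **Table 6-1.** State a minimum dose. For 80 and 60 mg entrants, give either a permitted lower step or discontinuation. The sponsor's clinical team should set the minimum. A plain minimum of 80 mg would exclude the 60 mg entry dose, so that group needs its own line.

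The cost is a protocol clarification or amendment to two tables, one footnote and one bullet. No extra data or participants are needed.
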